• A concentration average will be plotted for a given sampling time only if 2/3 of the individual data at the time point have quantifiable measurements that are within the sampling time window specified in the protocol or ± 10%. An average concentration estimated with less than 2/3 but more than 3 data points may be displayed on the mean concentration plot if determined to be appropriate and will be documented within the final study report.

Treatment of Outliers during Pharmacokinetic Analysis

Application of this procedure to all PK analyses is not a requirement. Rather, this procedure provides justification for exclusion of data when scientifically appropriate. This procedure describes the methodology for identifying an individual value as an outlier for potential exclusion, but does not require that the value be excluded from analysis. The following methodology will not be used to exclude complete profiles from analysis.

Data within an Individual Profile

A value within an individual profile may be excluded from analysis if any of the following criteria are met:

- For PK profiles during multiple dosing, the concentration of the pre-dose sample exceeds all measured concentrations for that individual in the subsequent post-dose samples.
- For PK profiles during single dosing of non-endogenous compounds, the concentration in a pre-dose sample is quantifiable.
- For any questionable datum that does not satisfy the above criteria, the profile will be evaluated and results reported with and without the suspected datum.

Data between Individual Profiles

- 1. If n < 6, then the dataset is too small to conduct a reliable range test. Data will be analyzed with and without the atypical value, and both sets of results will be reported.
- 2. If n≥6, then an objective outlier test will be used to compare the atypical value to other values included in that calculation:
 - a. Transform all values in the calculation to the logarithmic domain.
 - b. Find the most extreme value from the arithmetic mean of the log transformed values and exclude that value from the dataset.
 - c. Calculate the lower and upper bounds of the range defined by the arithmetic mean $\pm 3^{*}$ SD of the remaining log-transformed values.
 - d. If the extreme value is within the range of arithmetic mean ± 3 *SD, then it is not an outlier and will be retained in the dataset.

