e. If the extreme value is outside the range of arithmetic mean ± 3 *SD, then it is an outlier and will be excluded from analysis.

If the remaining dataset contains another atypical datum suspected to be an outlier and $n \ge 6$ following the exclusion, then repeat step 2 above. This evaluation may be repeated as many times as necessary, excluding only one suspected outlier in each iteration, until all data remaining in the dataset fall within the range of arithmetic mean ± 3 *SD of the log-transformed values.

Reporting of Excluded Values

Individual values excluded as outliers will be documented in the final report. Approval of the final report will connote approval of the exclusion.

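### SAP 9.3.1 gives two answers on whether a flagged between-profile PK outlier is excluded, and its n ≥ 6 branch does not ask for results with and without the value

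*SAP*

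**What the plan says.** SAP 9.3.1, under Treatment of Outliers during Pharmacokinetic Analysis, opens with a preamble. It says "Application of this procedure to all PK analyses is not a requirement". It presents the procedure as a justification for exclusion where that is scientifically appropriate, and adds that identification "does not require that the value be excluded from analysis". It also protects whole profiles: "The following methodology will not be used to exclude complete profiles from analysis".

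Three rules for questionable values follow:

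- **Within a profile**, for a questionable value that meets none of the listed criteria: "the profile will be evaluated and results reported with and without the suspected datum".
- **Between profiles, n < 6** (step 1): "Data will be analyzed with and without the atypical value, and both sets of results will be reported".
- **Between profiles, n ≥ 6** (step 2): "an objective outlier test will be used to compare the atypical value to other values included in that calculation". The most extreme log value is set aside and the mean ± 3 SD of the rest is calculated. If the extreme lies outside that range, "then it is an outlier and will be excluded from analysis". On further suspected values: "This evaluation may be repeated as many times as necessary", as long as n stays at 6 or more.

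Excluded values must be documented in the final report. SAP 9.1 requires listings of all data in the database and names the geometric mean and geometric CV as summaries for AUC and Cmax. SAP 9.3.2 summarizes each regimen separately. SAP 7 targets 8, 10 and 10 completers.

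**The concern.** There are two problems. First, after a positive test the preamble leaves exclusion open and step 2e does not. Two analysts could follow the same SAP on the same data and report different geometric CVs. Second, the safeguard of reporting both sets of results is given to the smallest groups and to within-profile questions. It is missing from the branch that the planned groups will normally use.

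PK is the primary objective, and protocol 5.2 says these results will be compared with PK in non-Chinese patients. Removing an extreme value always narrows the reported spread. If the value is genuine, the between-patient variability carried into that comparison will usually be too small, and no all-data summary is required beside it.

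**Working it through.** **Which branch applies.** Planned completers are 8 (single dose), 10 (Q2W) and 10 (Q4W). Enrolment of up to 15 and 30, randomized 1:1 in the multiple-dose phase, gives at most about 15 per group. All are at least 6. The SAP's n, however, is the number of values in the calculation concerned, so a sparsely estimable parameter can fall below 6.

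**How far the SD must fall after one removal (exact).** Let S be the SD of all n log values, s the SD of the other n − 1, and d the distance of the extreme from their mean. Then

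(n − 1)S² = (n − 2)s² + ((n − 1)/n)d².

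Step 2e removes the value only if d > 3s. At d = 3s,

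s/S = √[(n − 1) / ((n − 2) + 9(n − 1)/n)],

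and any larger d gives a smaller ratio.

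| n | Numbers put in | Largest possible s/S |
|---|---|---|
| 8 | √[7/(6 + 7.875)] | 0.710 |
| 10 | √[9/(8 + 8.1)] | 0.748 |
| 15 | √[14/(13 + 8.4)] | 0.809 |

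This needs no assumption about the distribution or about how often the test is run.

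**How often a genuine value is removed.** The lower end is 0%, because the test is optional and starts from a value judged atypical, a term the SAP does not define. For the upper end, assume clean log-normal data and the test run once on every set:

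rate ≈ n × P(|t with n − 2 df| > 3/√(1 + 1/(n − 1))).

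| n | t cut-off | Formula | Simulated (400,000 sets) |
|---|---|---|---|
| 8 | 2.81 | 24.7% | 24.6% |
| 10 | 2.85 | 21.6% | 21.6% |
| 15 | 2.90 | 18.7% | 18.6% |

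**Typical size when a clean set loses one value.** The mean s/S is 0.614, 0.669 and 0.754 at n = 8, 10 and 15. Repeating the test automatically, which the SAP permits but does not require, gives 0.53, 0.60 and 0.71.

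**On the geometric CV scale.** The documents give no CV, so true values of 30%, 40% and 50% are assumed. Geometric CV = 100√(exp(SD²) − 1). Simulated means, good to about 0.1, in sets with one removal:

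| Assumed true CV | n = 8, all data → after removal | n = 10, all data → after removal |
|---|---|---|
| 30% | 29.0 → 17.6 | 29.2 → 19.3 |
| 40% | 38.8 → 23.2 | 39.0 → 25.5 |
| 50% | 48.7 → 28.7 | 48.9 → 31.6 |

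Averaged over all sets, with and without a removal, the upper-end effect at an assumed 40% is 38.8 → 35.0 (n = 8) and 39.1 → 36.2 (n = 10).

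**The case against.** The best defence is that the preamble governs the whole section. The procedure is optional and rests on scientific judgement, and step 2e merely states the outcome of the test inside it. That settles whether to run the test. It does not settle what follows a positive result, because the preamble's statement about exclusion concerns the identified value itself. The within-profile rule is worded permissively, so the SAP uses permissive language where it intends it. The mismatch stands, though one sentence would cure it.

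The defence is right to resist several stronger readings:

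- *Every planned calculation falls in the n ≥ 6 branch.* Not so. Half-life is reported only when a reliable estimate exists, and other parameters only when possible. Such calculations can drop below 6 and then get both sets of results.
- *About a quarter of groups will lose a valid value.* The documents do not support this. That figure is the upper end, reached only if the test is run on every clean set.
- *The CV is understated whenever a genuine value goes.* That is exact against the all-data CV. Against the true SD it fails in about 2%, 3% and 5% of flagged clean sets at n = 8, 10 and 15.
- *The 3-SD limit is itself an error because it is tighter than a 5% Grubbs test.* The SAP claims no 5% level, and leaving the extreme out of the SD is a fair answer to masking.

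The safeguards are also real. Exclusions are documented, data are listed and whole profiles are kept, so a reader could rebuild the all-data summary. The SAP does not oblige the sponsor to present it.

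**Conclusion.** The concern holds as an inconsistency plus a reporting gap. SAP 9.3.1 does not say with one voice whether a value that fails the test leaves the analysis. Where n ≥ 6 it does not require the all-data summary that it requires at n < 6.

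The assumption-free part of the size is the ceiling on the log SD after one removal: 71%, 75% or 81% of the all-data value. The frequency (0% to 25%, 22% or 19%) rests on log-normal data and a discretionary trigger, and the CV figures rest on assumed true CVs.

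Impact is minor to moderate. The analysis is descriptive, SAP 7 sets no statistical requirement on the sample size, and the comparison with non-Chinese patients has no stated acceptance criterion. A reader might infer that exclusions are hidden or that the geometric mean is biased. Neither follows: exclusions must be documented, and the geometric mean can move either way with no systematic direction. It is still worth correcting, because a pre-specified rule for the primary-objective data should have one reading.

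**What to change.** In SAP 9.3.1 step 2e, replace the exclusion wording with: *will be flagged as an outlier for potential exclusion*. Add that PK summaries will be reported with and without any flagged value at every n, as step 1 already requires for n < 6. As a consequential edit, the paragraph on repeating the test should say that a flagged value is set aside only for the next round of testing.

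The cost is a short wording change and one extra summary when a value is flagged. The all-data CV may be larger than the one after exclusion. No change to sample size, design or conduct is needed. A size-adjusted limit, or a rule on which of the two summaries is primary, is optional and not needed to correct the error.

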9.3.2 Pharmacokinetic Statistical Methodology

Descriptive statistics of PK parameters will be presented for each dose regimen (single-dose, Q2W multiple-dose, and Q4W multiple-dose) separately.

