9.2. Treatment Administration

This study involves an evaluation of ixekizumab 80 mg administered by prefilled syringe during the treatment period. For the single-dose phase, all patients will receive a single dose of 80 mg given as one 80 mg SC injection at Week 0 (Visit 2) and will then be observed for a 20-week period. For the multiple-dose phase, all patients will receive a 160 mg SC starting dose (2 injections) and will then be randomized at a 1:1 ratio to 1 of 2 dose groups via a computer-generated random sequence using an interactive web-response system (IWRS): one group will receive 80 mg SC Q2W starting on Day 15, and the other group will receive 80 mg SC Q4W starting on Day 29 for the duration of the 8-week treatment period. All patients in the multiple-dose phase will be followed for an additional 20-week observation period after the treatment period completes.

Injections will be administered at the site by the clinical staff.

Administration: A dose of investigational product will consist of SC injection(s) of investigational product. Possible injection sites include the abdomen, thigh, and upper arm. The injection site should not be in a psoriatic lesion and should be rotated to another area for subsequent doses.

Allow the prefilled syringe containing the drug product to equilibrate to room temperature for approximately 30 minutes. Do not return syringe to the refrigerator.

The investigator or designee is responsible for:

- explaining the correct use of the investigational agent to the site personnel,
- verifying that instructions are followed properly,
- maintaining accurate records of investigational product dispensing and collection,
- and returning all unused medication to Lilly or its designee at the end of the study.

Note: In some cases, sites may destroy the material if, during the investigator site selection, the evaluator has verified and documented that the site has appropriate facilities and written procedures to dispose clinical trial materials.

Patients will be instructed to contact the investigator as soon as possible if he or she has a complaint or problem with the investigational product so that the situation can be assessed. See Section 10.4.5 for more details.

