11.2.4. Pharmacokinetic Analyses

Pharmacokinetic parameter estimates for ixekizumab will be calculated by standard noncompartmental methods of analysis. The PK parameters for estimation after the single dose will include C_{max} , time to C_{max} (t_{max}), and area under the concentration versus time curve (AUC). Other parameters such as terminal half-life, apparent clearance, and apparent volume of distribution may be determined. The PK parameters for estimation after the last dose of the 8-week treatment will include C_{max} , t_{max} , and AUC. Other parameters such as terminal half-life, apparent clearance, and apparent volume of distribution may be determined.

Descriptive statistics of PK parameters will be presented for each dose regimen (single dose, Q2W multiple dose, and Q4W multiple dose). Data may also be analyzed by population PK methods alone or in combination with other studies as deemed appropriate.

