6. TREATMENTS

The following is a list of the study treatment abbreviations that will be used in the TFLs.

Study Treatment Name	Treatment order in TFL
Ixekizumab 80 mg Single Dose	1
Ixekizumab 160 mg Starting Dose /80 mg Q2W	2
Ixekizumab 160 mg Starting Dose /80 mg Q4W	3

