9.3 Pharmacokinetic Assessment

9.3.1 Pharmacokinetic Analysis

Noncompartmental methods will be applied using a validated software program (Phoenix WinNonlin Version 6.4 or later) to analyze the serum concentrations of ixekizumab and determine the PK parameters of ixekizumab.

Single-Dose Phase

Following the 80 mg in the single dose phase, the following PK parameters will be determined, when possible:

Statistical Analysis Plan Version 2 Covance Clinical Study No. 8346599

Parameter	Units	Definition
AUC(0-t _{last})	µg.day/mL	area under the concentration versus time curve from time zero to time t, where t is the last time point with a measurable concentration
AUC(0-∞)	μg.day/mL	area under the concentration versus time curve from zero to infinity
%AUC(tlast-∞)	%	percentage of $AUC(0-\infty)$ extrapolated
C _{max}	μg/mL	maximum observed drug concentration
t _{max}	day	time of maximum observed drug concentration
t _{last}	day	time of last observed drug concentration
t _{1/2}	day	half-life associated with the terminal rate constant (λz) in non- compartmental analysis
CL/F	L/h	apparent total body clearance of drug calculated after extra-vascular administration
V_Z/F	L	apparent volume of distribution during the terminal phase after extra-vascular administration
V _{SS} /F	L	apparent volume of distribution at steady state after extra-vascular administration

Multiple-Dose Phase

Serum concentrations of ixekizumab following single dosing of 160 mg on Day 1 (i.e. up to 14 days post the first dose and prior to the second ixekizumab dose), will be used to determine the single dose PK parameters and will be a subset of the parameters listed above that can be calculated based on only 14 days worth of sampling. Serum concentrations of ixekizumab from Week 8 following the last dose of repeated dosing of ixekizuamb will be used to determine the following multiple-dose PK parameters, when possible:

Parameter	Units	Definition
AUCτ	μg.day/mL	area under the concentration versus time curve during one dosing interval
C_{max}	µg/mL	maximum observed drug concentration
t _{max}	day	time of maximum observed drug concentration
t _{1/2}	day	half-life associated with the terminal rate constant (λz) in non- compartmental analysis
CL/F	L/h	apparent total body clearance of drug calculated after extra-vascular administration
V_Z/F	L	apparent volume of distribution during the terminal phase after extra-vascular administration

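### First-dose 160 mg PK is one exposure common to both multiple-dose arms, but the SAP defines only by-regimen summaries and no pooled 160 mg group

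*SAP*

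**What the plan says.** Protocol 9.2 gives every multiple-dose patient the same first dose: "all patients will receive a 160 mg SC starting dose (2 injections) and will then be randomized at a 1:1 ratio". Treatment first differs two weeks later, when "one group will receive 80 mg SC Q2W starting on Day 15" while the other arm is not dosed again until Day 29.

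SAP 9.3.1 adds a first-dose analysis for this phase. It uses "Serum concentrations of ixekizumab following single dosing of 160 mg on Day 1 (i.e. up to 14 days post the first dose" and before the second dose, and reports whichever single-dose parameters "can be calculated based on only 14 days worth of sampling". The 14-day limit applies to both arms, although the Q4W arm goes 28 days before its next dose.

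For reporting, SAP 9.3.2 contains a single rule: "Descriptive statistics of PK parameters will be presented for each dose regimen (single-dose, Q2W multiple-dose, and Q4W multiple-dose) separately". Protocol 11.2.4 uses the same three groups. In SAP 6 the starting dose appears only inside the two regimen labels, for example "Ixekizumab 160 mg Starting Dose /80 mg Q2W", and the label containing the words Single Dose is the 80 mg one.

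**The concern.** The SAP's derivation treats the starting dose as one exposure, while its reporting rule splits it by a regimen that has not yet begun to differ. Apart from chance, nothing should separate the two arms' first-dose Cmax, tmax or 14-day AUC.

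The multiple-dose phase supplies the study's only data on 160 mg. Protocol 5.2 says that PK in Chinese patients will be compared with PK from global studies. The one figure the protocol gives for this dose, in footnote a of Table RHBN.1 (Protocol 9.3), is a single model-predicted AUC over 168 hours of 1.987 mg·hr/mL, not divided by later regimen. The natural counterpart is one estimate from all patients given 160 mg. The plan would produce two, each with half the patients, differing by chance.

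**Working it through.** **Planned numbers (SAP 7; Protocol 11.1).** Enrolment: 15 + 30 = 45, as stated. Multiple-dose completers at 1:1: 20 × ½ = 10 per regimen, as stated. At maximum enrolment: 30 × ½ = 15 per regimen. There is no alpha, power or effect size to reproduce.

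**Are the arms the same up to the Day 15 sample?** (Protocol 9.2 and Attachment 2)
- Dose: 160 mg on Day 1 in both arms.
- PK samples: Days 1 (pre-dose), 3, 5, 8, 11 and 15, with no arm restriction. The only Q2W-specific PK sample is at Visit 10 (Day 43), footnote k.
- Day 15: footnote j puts the sample before the dose in the Q2W arm; the Q4W arm has no dose that day. The ±1 day visit tolerance is common to both.

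So the first-dose window closes before the regimens diverge.

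**Precision of a geometric mean.** Log-scale half-width h = t(0.975, n−1) × s/√n, with s = √ln(1 + CV²). The factor t/√n does not depend on CV:
- n = 10: 2.262/√10 = 0.715; n = 20: 2.093/√20 = 0.468; ratio 0.65, so 35% narrower.
- n = 15: 2.145/√15 = 0.554; n = 30: 2.045/√30 = 0.373; ratio 0.67, so 33% narrower.

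The documents give no between-patient CV for these parameters, so 20% to 60% is assumed. At CV 40%, s = √ln 1.16 = 0.385, and h = 0.276 (n = 10), 0.180 (n = 20), 0.213 (n = 15) and 0.144 (n = 30). The 95% intervals, as multiples of the geometric mean, are:

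| Assumed CV | n = 10 | n = 20 | n = 15 | n = 30 |
|---|---|---|---|---|
| 20% | 0.868–1.152 | 0.911–1.097 | 0.896–1.116 | 0.929–1.077 |
| 40% | 0.759–1.317 | 0.835–1.198 | 0.808–1.238 | 0.866–1.155 |
| 60% | 0.673–1.487 | 0.771–1.296 | 0.736–1.359 | 0.813–1.230 |

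**Chance difference between the two displayed estimates.** The SD of the log ratio of two arm geometric means is s√(2/n). At CV 40% and n = 10 this is 0.385 × √0.2 = 0.172. Taking 0.80–1.25 purely as a yardstick (neither document sets one for this comparison), ln 1.25/0.172 = 0.223/0.172 = 1.30. Under identical treatment the ratio therefore falls outside that range with probability about 20%. At n = 15 the SD is 0.141, the quotient 1.59 and the probability about 11%.

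**The case against.** The case against is substantial, and most of it limits the size of the point.

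- **The split is partly inferred.** SAP 9.3.2 never names the first-dose parameters, SAP 6 lists labels without forbidding a pooled column, and SAP 3 leaves table layout to a shell document that was not available and may already pool. This stands. But the SAP text itself defines no pooled 160 mg group on any reading, because its single-dose category is the 80 mg treatment.
- **Nothing is discarded.** A reader might infer that half the data are thrown away. They are not: both arms are summarised and all data listed. From each arm's N, geometric mean and geometric CV, the pooled values can be recovered to within rounding, and Protocol 11.2.4 allows population PK analysis of all the data. The loss is in the precision of each reported summary.
- **No interval or test is planned.** SAP 9.1 lists descriptive statistics only, and SAP 7 disclaims any statistical basis for the sample size. The interval widths above measure information; they are not planned outputs.
- **Ten per arm is not the firm denominator.** It is the target for completing the whole phase. The PK population in SAP 8 includes everyone dosed with evaluable PK data, so the number for a 14-day window could reach about 15 per arm. The relative gain barely changes; the absolute imprecision is smaller.
- **Protocol-named primary parameters are not affected.** A reader might infer that they are. Protocol 11.2.4 names parameters after the single dose and after the last dose; the 160 mg first-dose set is a SAP addition under the general PK objective. No method is specified for the comparison with global PK, so nothing shows that it depends on this table.
- **By-arm first-dose results have a use.** They allow first-dose and Week 8 exposure to be compared within the same arm and show chance imbalance between small groups. Replacing them would be a loss, so they should stay.

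**Conclusion.** The point holds as a minor gap in reporting. The SAP derives first-dose 160 mg parameters over a window in which the two arms are indistinguishable by design, then provides only for separate regimen summaries. Pooling would replace two groups of about 10 to 15 with one of 20 to 30 and narrow a log-scale 95% interval by 33% to 35% at any CV. The absolute widths rest on an assumed CV, log-normality and equal arm sizes. The conclusion also assumes that the table shells do not already contain a pooled column; if they do, only the SAP wording needs to catch up. No planned inference or decision is shown to be at risk.

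**What to change.** In SAP 6 and 9.3.2, add a reporting group such as *160 mg starting dose, both arms, Day 1 to pre-dose Day 15*. Make it the main summary for first-dose PK parameters and for the mean concentration profile to Day 15. Keep the by-arm first-dose columns as supportive, and keep Week 8 parameters by regimen.

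State that the existing SAP 9.3.1 evaluation of quantifiable Day 1 pre-dose concentrations applies to patients who roll over from the single-dose phase, so that carried-over drug is handled the same way in pooled and by-arm summaries.

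The cost is SAP wording and a change to the table and figure shells. Dosing, sampling, visits and enrolment are unaffected.
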